5.4 Sample acquisition, storage and transport

Please refer to the laboratory manual.

Dried blood spot, serum, plasma and tissue blocks collection and initial processing (labelling, handling, completing sample tracking log) will be performed at trial sites and will then be transferred for further processing in CMDL or QMUL.

Remining tissue blocks, after study is ended, will be transported for further storage to the biorepository.

All samples will be fully tracked from site, to laboratory, to biorepository using sample tracking logs.

5.5 Data collection

All information will be collected on standard proformas (Table 1) and identified by study number, initials and date of birth. Registration Form, Participant Baseline CRF, Surgery CRF, and Outcome CRF will be entered by the relevant site directly into the study database in REDCAP via a web interface. Sites are also permitted to enter study data into paper CRFs when needed.

We aim to collect a minimal demographic dataset including age, ethnicity, parity, GP details and significant medical/surgical history. We aim to use the NHS number as the primary identifier when linking to national registries and to track individuals throughout the NHS. Some additional data will be collected at follow-up.

Data will be collected on relevant medical, obstetric and gynaecological, surgical history, emotional impact as well as information on the symptoms that prompted GP referral or investigation. USG information will be collected. Data on the reference diagnosis will be obtained from the histopathology form and a structured template to assess wellbeing for participants who do not undergo surgery will be developed in association with the participating sites.

5.6 Death

If a participant dies prior to histology data being provided (if available), inform Study Office immediately via a Change of Status form.

5.7 Analysis

5.7.1 Test accuracy

We will compare ctDNA to Risk of malignancy index 1 (RMI 1) as an alternative test used at this point in the patient pathway in clinical practice as specified in primary outcome. All test comparisons will be in relation to the reference test results, so the comparative accuracy of tests to detect ovarian cancers can be calculated. We will report estimates of sensitivity, specificity, PPV and NPV. Imputation will be used to account for missing data and imperfect reference data.

5.7.2 Primary outcome

Comparison of sensitivity and specificity of ctDNA to RMI 1 at threshold of 250 for early stage (stage I/II) high grade serous ovarian cancer (HGSOC) in postmenopausal women.

- Of 500 women, with an expected 5% loss of follow up, and 10 - 15% not referred for surgery or biopsy we expect to analyse approximately 406 cases. Given a prevalence (from our experience in ROCKETTS-GEN) of 27% we expect to observe 110 ovarian cancers, ~50% of which will be Stage 1-2 and ~50% stage 3-4. Of the 110 ovarian cancers, 70% would be expected to be HGSOC, of these 25% to be early stage. Blood packs will be posted for central processing.

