2 ROCKETS GEN V2 STUDY DESIGN

2.1 Aim of the study

- To evaluate plasma ctDNA as a diagnostic test with increased sensitivity and specificity compared to serum CA125 for earlier diagnosis of ovarian cancer in postmenopausal women.
- To collect representative blocks from resected tumour tissue to establish a translational resource for future early detection research.
- To collect dried blood spots and serum for analysis of circulating biomarkers and blood ctDNA in cohorts of women at high risk of ovarian cancer, to establish improved diagnostic test for postmenopausal women.

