2.2 Design

ROCKETS GEN V2 study is a prospective single arm cohort diagnostic accuracy study where all patients receive all tests and accuracy of tests is evaluated against a gold standard of histology or 12-month outcome.

A test accuracy study compares measurements obtained by index tests with those obtained by a reference standard. In this way the accuracy of index tests can be estimated. A reference standard is a test (or combination of tests) that confirms or refutes the presence or absence of disease beyond reasonable doubt.

Here, the reference standard will be histology or cytology of tissues taken from patients who proceed to surgery or biopsy, or in patients who do not undergo surgery or biopsy assessment of cancer/non cancer outcomes determined from hospital records at 12 months. The diagnostic performance of the index test will be compared against that of the comparator test – the existing standard risk prediction score RMI 1. RMI combines CA125 and limited ultrasound features to provide a score that is used to determine patient management.^{3,37}

ROCKETS GEN V2 will recruit postmenopausal women at 'low' or unknown genetic risk of ovarian cancer i.e. not women known to have a BRCA1/2 or other germline mutation predisposing to ovarian cancer.

Recruited women will have the following tests and follow up recorded:

- CA125 (if not performed already as part of standard care).
- IOTA transvaginal ultrasound and additional abdominal scan if performed as part of standard care
- Histology result where biopsy or surgery is clinically indicated
- 12 month follow up status ascertained by research team using hospital records, a telephone call or by contacting GP.
- Women entering ROCKETS-GEN V2 will donate dried blood spots, blood samples for plasma and serum analysis at recruitment. Women undergoing surgery for ovarian pathology will also be consented to donate tissue block/s of representative tissue for research.

Representative tissue block/s and slide will be retrieved from pathology labs and proceeding to undergo surgery as part of standard care. These blocks will first undergo specialist pathology review by an expert gynaecological pathologist. DNA will then be extracted from cancer tissues for additional analyses including shallow whole genome sequencing.

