2.8 Sample size

Sample size will be 500 newly presenting postmenopausal women blood samples, allowing 5% for loss to follow up.

The Cancer Molecular Diagnostics Laboratory (CMDL) and Queen Mary University of London (QMUL) teams performing plasma ctDNA analysis and additional biomarker analysis will be blinded to the clinical dataset held at UoB. This is to eliminate bias in analysis of the samples and to test the validity of the biomarker. To ensure this the clinical dataset will be maintained in UoB and the team at UoB will supply research teams with the samples anonymised with participant study numbers only. Research teams will send UoB the results of the analysis and the UoB and statistical team will then check that against outcome data to analyse trial outcomes.

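### The protocol sets the RMI comparator's cut-off at 200 in Section 2.5 and at 250 in the primary outcome (Section 5.7.2), and the two must be reconciled

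*Protocol*

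**What the plan says.** Five places in the protocol bear on the comparator.

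- **Section 2.5 (Comparator).** A one-line entry that sets the comparator as RMI with a cut-off of 200.
- **Section 5.7.2 (Primary outcome).** "Comparison of sensitivity and specificity of ctDNA to RMI 1 at threshold of 250", and then "for early stage (stage I/II) high grade serous ovarian cancer (HGSOC) in postmenopausal women".
- **Section 2.2 (Design).** The comparator test is "the existing standard risk prediction score RMI 1", described as combining CA125 with limited ultrasound features. No cut-off is given.
- **Section 5.7.1 (Test accuracy).** ctDNA will be compared with RMI 1 "as specified in primary outcome". Sensitivity, specificity, PPV and NPV will be reported.
- **Section 2.1 (Aim).** The first aim is a ctDNA test with "increased sensitivity and specificity compared to serum CA125". RMI is not mentioned there.

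No other section gives an RMI cut-off. None assigns 200 and 250 to different analyses, and none states that one section overrides the other.

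**The concern.** A score with two cut-offs is two different binary tests. The primary outcome compares ctDNA with RMI 1 on both sensitivity and specificity, so the cut-off decides which women count as RMI-positive and therefore what ctDNA is measured against. A higher cut-off can only make the sensitivity target easier for ctDNA or leave it unchanged. A lower one does the same for the specificity target. While both values stand in current text, either could be defended from the protocol after the results are known.

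The other safeguards do not close this gap. Section 2.8 blinds the laboratories to clinical data, but the university and statistical team then set the results against outcomes. Section 5.7.3 locks the ctDNA analysis code and does not mention the RMI cut-off. This is a remark about a choice left unfixed, not about anyone's intent.

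**Working it through.** **1. Are the two statements about the same test?** Section 2.5 says RMI and Section 5.7.2 says RMI 1. Section 2.2 names RMI 1 as the comparator, so the difference in label does not explain the difference in cut-off. Both statements are current text.

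**2. Does any section settle it?** Section 5.7.1 refers the reader to the primary outcome, and so to 250. That is a pointer within the analysis section, not a precedence rule. Section 2.5 still states 200 for the study as a whole.

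**3. What depends on the cut-off?** Every woman positive at 250 is also positive at 200, so moving from 200 to 250 has these effects:

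- true positives cannot increase, so RMI sensitivity cannot rise;
- false positives cannot increase, so RMI specificity cannot fall;
- RMI's PPV and NPV, and the contrasts with ctDNA, change if any woman is reclassified in a way that alters them;
- ctDNA's own sensitivity and specificity do not depend on it.

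All RMI quantities stay the same if nobody scores between the two values.

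**4. The protocol's own counts.** The inputs are "Sample size will be 500 newly presenting postmenopausal women blood samples, allowing 5% for loss to follow up" (Section 2.8), then "10 - 15% not referred for surgery or biopsy we expect to analyse approximately 406 cases" and "of 27% we expect to observe 110 ovarian cancers" (Section 5.7.2).

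- Analysed women: 500 x 0.95 x 0.85 = 403.75 with 15% not having surgery or biopsy, and 500 x 0.95 x 0.855 = 406.1 with 14.5%. The stated 406 is reproduced near the upper end of the 10 to 15% range; 10% would give 427.5.
- Ovarian cancers: 406 x 0.27 = 109.6, which rounds to the stated 110.
- HGSOC at the stated 70%: 110 x 0.70 = 77.
- Early-stage HGSOC at the stated 25%: 77 x 0.25 = 19.25, or about 19 women.

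None of these counts depends on the RMI cut-off.

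**5. Effect per reclassified woman.** With 19 target cases, each one scoring between the cut-offs changes RMI sensitivity by 1/19 = 5.3 percentage points. (Whether a score exactly at a cut-off counts as positive sets the ends of that band.)

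**6. What cannot be computed.** The protocol gives no distribution of RMI scores, so the number of women in the band is unknown and may be zero. It also states no alpha, power or effect size for this comparison, so there is no power figure to recompute under either cut-off.

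**The case against.** The strongest reply is that the primary outcome has one stated cut-off. Section 5.7.1 sends the reader to Section 5.7.2, which says 250, and Section 2.5 is a brief design entry that does not mention the primary outcome. This has weight, and it is why the choice should not be described as wholly open. It does not dispose of the point. Section 2.5 is headed as the comparator for this study, gives a different number, and is not said to serve another analysis. Nor can the matter be left to a statistical analysis plan, because a plan adopting either value would contradict one section of the protocol.

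Four stronger readings are tempting, and the documents do not support them.

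- **CA125 as a third version of the primary comparison.** A reader might infer this from aim 1. Sections 2.2, 5.7.1 and 5.7.2 offer only RMI 1 for that comparison. The mismatch between aim and outcome is real but separate and lesser, and a CA125 cut-off could properly sit in the analysis plan.
- **All primary quantities are undefined.** Only RMI's accuracy and the contrasts with ctDNA are affected.
- **A large shift in RMI sensitivity.** Two women in the band would give 2/19 = 10.5 points and three would give 3/19 = 15.8, but nothing in the protocol indicates that any woman will fall there. These are illustrations, not forecasts.
- **Any second cut-off can be applied later at no cost because the score is held as a number.** No section says that the RMI score is recorded. Table 1 in Section 2.10 makes the ultrasound CRF optional, Section 3.2.1 allows entry on a raised CA125 before imaging, and Section 5.5 says only that ultrasound information will be collected.

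**Conclusion.** The contradiction stands. The threshold that defines the comparator in the primary outcome is given as 200 in one section and 250 in another, for the same score, with no rule that reconciles them. It should be corrected before ctDNA results are merged with outcomes.

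Its size can be stated only per woman: about 5.3 percentage points of RMI sensitivity for each early-stage HGSOC between the two values. That rests on the protocol's planning figures of 110 cancers, 70% HGSOC and 25% early stage being met. The total effect cannot be derived and may be nil. The direction is certain only in the weak sense that 250 cannot give RMI higher sensitivity or lower specificity than 200. The documents do not establish which value was intended, and this point takes no position on that.

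**What to change.** State one RMI 1 cut-off in identical terms in Sections 2.5 and 5.7.2, and use the label RMI 1 in both. Do this before any ctDNA result is merged with outcome data. The sponsor must decide which value is meant.

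Reporting the other cut-off is optional. If it is reported, label it as secondary, and first confirm that the RMI score or its components are captured for each participant.

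As a separate and lesser edit, align aim 1 in Section 2.1 with the RMI 1 comparator, or name ctDNA versus CA125 as a secondary comparison.

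The cost is a wording amendment. Reconciling the two sections does not change the recruitment target, since none of the stated counts depends on the cut-off. Checking that RMI is captured is a further small task, and it could lead to a CRF change if the components prove not to be collected.

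### The projected 406 analysed for the primary outcome leaves out women not referred for surgery or biopsy, to whom the design gives a 12-month reference standard; the two must be reconciled

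*Protocol*

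**What the plan says.** Section 2.2 (Design) sets a two-part reference standard: tissue diagnosis for women who have surgery or biopsy, and "in patients who do not undergo surgery or biopsy assessment of cancer/non cancer outcomes determined from hospital records at 12 months". Sections 2.7 and 5.2 repeat the 12-month assessment for women who do not have surgery. Table 1 schedules an Outcome CRF at 12 months for those without histology or cytology. Section 5.7.3 describes the reference standard as histology together with clinical follow-up.

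Section 2.8 names one source of attrition: "Sample size will be 500 newly presenting postmenopausal women blood samples, allowing 5% for loss to follow up".

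Section 5.7.2 projects the numbers for the primary outcome, the comparison of sensitivity and specificity of ctDNA with RMI 1. It begins "Of 500 women, with an expected 5% loss of follow up" and goes on to subtract the women without surgery or biopsy: "10 - 15% not referred for surgery or biopsy we expect to analyse approximately 406 cases". At a prevalence "of 27% we expect to observe 110 ovarian cancers".

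Two further statements bear on the point. Section 2.2 says that the components of RMI "provide a score that is used to determine patient management". Section 5.7.1 says "Imputation will be used to account for missing data and imperfect reference data", without saying whether women who have no tissue diagnosis are among those it covers.

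**The concern.** The design sections treat women without surgery or biopsy as having a reference result, and the study collects it. The projection for the primary outcome counts them as not analysed. Both cannot be the plan.

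The choice affects the specificity half of the primary comparison. RMI influences management and is also the comparator, so an analysis confined to women with tissue would select partly on the result of one of the two tests compared. That is partial verification. The ctDNA assay is analysed at the end of the study (section 2.2) and cannot influence referral, so the two tests would not be affected alike. If women managed without tissue are mostly cancer-free and RMI-negative, leaving them out removes RMI true negatives and moves the comparison towards ctDNA.

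The denominator also fixes the prevalence behind PPV and NPV (section 5.7.1) and the continuing review of prevalence and sample size (section 7.3).

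**Working it through.** **Inputs from the protocol.** 500 enrolled (2.8, 5.7.2); 5% loss to follow-up; 10-15% not referred for surgery or biopsy; 406 analysed; prevalence 27%; 110 cancers (all 5.7.2).

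**Reproducing 406.** Write d for the share not referred.

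- Loss to follow-up only: 500 × 0.95 = 475. This does not give 406.
- Sequential, 500 × 0.95 × (1 − d): 427.5 at d = 10%, 415.6 at 12.5%, 403.75 at 15%.
- Additive, 500 × (1 − 0.05 − d): 425 at 10%, 400 at 15%.
- The share that gives 406 exactly: 1 − 406/475 = 14.5%.
- Cancers: 406 × 0.27 = 109.6, stated as 110.

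So 406 is reached only by removing the non-referred women, near the 15% end of the range.

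**Women left out.** 475 − 406 = 69. Over the stated range: 475 × 0.10 = 47.5 to 475 × 0.15 = 71.25.

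**Denominators.**

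- Non-cancers in the projection: 406 − 110 = 296.
- If the 69 are all cancer-free: 296 + 69 = 365 non-cancers, and prevalence 110/475 = 23.2% instead of 27%.
- If 27% applied to all 475: 475 × 0.27 = 128 cancers.

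**RMI specificity (assumed values; the protocol gives none).** Let s be RMI specificity in the 296 with tissue and q the RMI-negative share among 69 cancer-free women without tissue. Specificity in all 365 is (296s + 69q)/365.

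- s = 75%, q = 100%: (222 + 69)/365 = 79.7%. The tissue-only figure is 4.7 points too low.
- s = 75%, q = 90%: (222 + 62.1)/365 = 77.8%, or 2.8 points too low.

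| s | understatement at q = 100% | understatement at q = 90% |
|---|---|---|
| 60% | 7.6 points | 5.7 points |
| 70% | 5.7 points | 3.8 points |
| 80% | 3.8 points | 1.9 points |
| 90% | 1.9 points | 0 |

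The bias is zero whenever q = s.

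**ctDNA minus RMI.** Assume s = 75%, q = 100%, and ctDNA specificity of 80% in the 296. The tissue-only difference is 80 − 75 = 5.0 points.

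- 80% of the 69 ctDNA-negative: ctDNA stays at 80.0%, and the full-cohort difference is 80.0 − 79.7 = 0.3 points.
- 90% of the 69 ctDNA-negative: ctDNA is (236.8 + 62.1)/365 = 81.9%, and the difference is 81.9 − 79.7 = 2.2 points.

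The tissue-only set overstates the ctDNA advantage by 4.7 points in the first case and 2.8 in the second.

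**Sensitivity.** If none of the 69 has cancer, the cancers are the same women in both sets and sensitivity does not change. The projected target group, from "Of the 110 ovarian cancers, 70% would be expected to be HGSOC, of these 25% to be early stage", stays at 110 × 0.70 × 0.25 = 19 women.

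**The case against.** The best defence is that 406 is a planning projection. It sits in a paragraph of expected numbers, defines no analysis set and excludes nobody by rule. The operative text on the reference standard (2.2, 5.7.3, Table 1) includes these women, and formal analysis sets may be in a statistical analysis plan that is not shown. This stands: a reader might infer that the protocol excludes the women and that the reported specificity will be biased, and the document does not go that far. It does not rescue the figure. If the women are to be analysed, 406 is not the number to be analysed.

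A second defence concerns the 27%. It comes from ROCKeTS-GEN, which section 1.5 describes as recruiting immediately before surgery, so applying it only to women with tissue is a coherent way to project cancers. A 12-month wellbeing check would also not by itself establish the histological type and stage that the primary target needs. Both arguments support projecting about 110 cancers. Neither is a reason to drop non-cancers from specificity.

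Third, the imputation sentence might be read as a further conflicting rule for the same women. It does not mention them, and it could be the intended correction for exactly this problem. It is unclear, and not shown to be a contradiction.

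Fourth, dependence on RMI is partial. Other management is left to local doctors under guidelines (4.4), entry already requires a raised CA125 or a lesion (3.2.1), and some women are recruited at preadmission or on the morning of surgery (3.1). This weakens the selection without removing it.

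Last, section 5.3 accepts shorter follow-up for women recruited in the final 12 months of recruitment, so 475 complete 12-month outcomes are not assured. That limits the gain but does not explain leaving out the whole group.

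**Conclusion.** The inconsistency is certain. Section 5.7.2 reaches about 406 only by removing women to whom sections 2.2, 2.7, 5.2 and Table 1 give a reference standard: about 69, or 48 to 71 at the stated 10-15%.

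The consequence is conditional. If the projected set is the one analysed, verification depends partly on the comparator, and RMI specificity is probably understated, by about 3 to 5 points when it is 75% in the women with tissue and 90-100% of the 69 cancer-free women are RMI-negative. These inputs are assumptions. The bias vanishes if RMI-negativity is equal in the two groups, and the distortion of the ctDNA-RMI difference is smaller if the 69 are also more often ctDNA-negative.

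A reader might also infer that RMI sensitivity is inflated. Nothing here shows that: it would need cancers among the women without tissue, and the calculation assumes none. The gain in precision is not an argument either. At 80% specificity the 95% half-width, 1.96 × √(0.8 × 0.2/n), moves only from 4.6 points (n = 296) to 4.1 (n = 365).

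**What to change.** In section 5.7.2:

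- State that the primary analysis set is all participants with a histology, cytology or 12-month outcome.
- Restate the count as up to about 475, with about 110 cancers and 365 non-cancers (prevalence about 23%) if the added women are cancer-free. Note that the 27% comes from a cohort recruited immediately before surgery.
- Keep the tissue-verified subset (about 404 to 428) as a sensitivity analysis.

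In section 5.7.1, say that imputation covers women whose outcome is missing or whose follow-up is cut short under section 5.3. Section 5.3 itself needs reconciling: it states 12 months of follow-up after the last recruit, and also says that the full 12 months will not be possible for late recruits.

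If the sponsor prefers the tissue-only set as primary, the protocol should justify the restriction and state how partial verification will be corrected.

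The cost is wording and one recalculated paragraph, since the Outcome CRF is already collected. The downside is that some negatives rest on follow-up and not on tissue, which the sensitivity analysis makes visible. It should be settled before test results are compared with outcomes, because choosing the set afterwards could change the head-to-head result.

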1 INTRODUCTION

1.1 Ovarian Cancer background

Ovarian cancer (OC) has an annual incidence of 7500 women and causes 4100 deaths annually in the UK; the lifetime risk of developing OC is 1 in 56.¹ 70% of patients will present at advanced stage and all stage, 5 year survival rate is around 45%. OC is predominantly a disease of older, post-menopausal women, however 1000 women under 50 will be diagnosed with OC annually.^{1,17} An international cancer benchmarking project shows OC survival in the UK is significantly lower than other western countries; it is unclear as to whether this could be attributed to delay in diagnosis or differences in treatment received.^{1,2}

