7.3 Statistical monitoring throughout the study

The prevalence of OC in the study will be constantly monitored and sample size calculations will be reviewed to check if the study has accrued enough samples and data to report.

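### Section 5.7.2: the overall stage split fits the HGSOC figures only if essentially all other ovarian cancers are early stage, and the roughly 19 women behind the primary sensitivity comparison are never stated

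*Protocol*

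**What the plan says.** Protocol section 2.8 gives the recruitment target: "Sample size will be 500 newly presenting postmenopausal women blood samples, allowing 5% for loss to follow up". Section 5.7.2 sets the primary outcome as a comparison of the sensitivity and specificity of ctDNA with those of RMI 1 for stage I/II HGSOC in postmenopausal women. It then builds the expected numbers:

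- "Of 500 women, with an expected 5% loss of follow up" and "10 - 15% not referred for surgery or biopsy", so that "we expect to analyse approximately 406 cases".
- With a prevalence of 27%, taken from ROCKeTS-GEN, "we expect to observe 110 ovarian cancers, ~50% of which will be Stage 1-2 and ~50% stage 3-4".
- Of those 110, "70% would be expected to be HGSOC, of these 25% to be early stage".

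The paragraph does not carry the calculation through to a number of stage I/II HGSOC. Section 7.3 says that "The prevalence of OC in the study will be constantly monitored and sample size calculations will be reviewed", the purpose being to judge whether enough samples and data have accrued to report. Section 1.1, as national background, says that "70% of patients will present at advanced stage".

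**The concern.** Two things in the paragraph need attention.

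First, it gives a stage split for all ovarian cancers and a separate stage split for HGSOC, the majority type. The first is far more favourable than the second, so the remaining cancers must make up the difference. There are not enough of them to do so comfortably.

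Second, the figures a reader sees are 406 women, 110 cancers and an implied 55 early-stage cancers. The group in which primary sensitivity is measured is much smaller and must be worked out. If oversight relies on the visible figures, it will overestimate how precisely sensitivity can be estimated. Section 7.3 names only overall ovarian cancer prevalence as the quantity to watch. That can be exactly on target while the number of stage I/II HGSOC is too small to say much about sensitivity.

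**Working it through.** **Inputs**, all from Protocol section 5.7.2: 500 recruited; 5% lost; 10 to 15% not referred for surgery or biopsy; 406 analysed; prevalence 27%; 110 cancers; about 50% stage 1-2; 70% HGSOC; 25% of HGSOC early.

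**1. Reproducing the protocol's totals.**
- 500 × 0.95 × 0.85 = 403.75 and 500 × 0.95 × 0.90 = 427.5. The stated 406 corresponds to 14.5% not referred: 500 × 0.95 × 0.855 = 406.1.
- 406 × 0.27 = 109.6, that is 110.

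Both totals stand.

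**2. Stage by type.**
- HGSOC: 110 × 0.70 = 77. Non-HGSOC: 110 − 77 = 33.
- Early HGSOC: 77 × 0.25 = 19.25. Advanced HGSOC: 77 − 19.25 = 57.75.
- At exactly 50%, advanced cancers of all types: 110 × 0.50 = 55. Advanced HGSOC alone exceeds this by 57.75 − 55 = 2.75.
- Equivalently, the non-HGSOC cancers would have to supply 55 − 19.25 = 35.75 early cancers out of 33, or 108%.
- Largest overall early share that the HGSOC figures allow: (19.25 + 33)/110 = 47.5%.

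**3. What a looser reading of the split requires.** The share of non-HGSOC that must be early is (110 × s − 19.25)/33, where s is the overall early share.

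| Overall early share | Non-HGSOC that must be early |
|---|---|
| 50% | 35.75 of 33 (108%) |
| 47.5% | 33 of 33 (100%) |
| 45% | 30.25 of 33 (92%) |
| 40% | 24.75 of 33 (75%) |

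**4. The count behind primary sensitivity.**
- Expected number: 110 × 0.70 × 0.25 = 19.25, about 19.
- Sampling range: binomial with n = 406 and probability 0.27 × 0.70 × 0.25 = 0.04725. The 2.5% and 97.5% points are 11 and 28.

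**5. Precision of sensitivity at 19 women** (95% Wilson interval).
- 10 of 19 detected (53%): 32% to 73%.
- 13 of 19 detected (68%): 46% to 85%.

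The half-width is about 20 percentage points.

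**6. Precision of specificity.** This rests on women without the target condition, including 406 − 110 = 296 without ovarian cancer, so the small count does not limit it.

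**7. Illustration of power.** The protocol states no significance level, target difference or discordance, so the following are assumptions: two-sided 5% exact McNemar test, sensitivity 75% against 50%, n = 19.

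| Assumed discordance (ctDNA only / RMI only) | Power |
|---|---|
| 37.5% / 12.5% (tests independent given disease) | 23% |
| 30% / 5% | 29% |
| 25% / 0% | 33% |

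**The case against.** The strongest reply is that the split is marked as approximate. The gap is 2.5 percentage points, and modest rounding closes it: 70% HGSOC with 30% early allows an overall early share of 0.30 + 0.70 × 0.30 = 51%, and 65% with 25% allows 0.35 + 0.65 × 0.25 = 51.25%. This stands to the extent that the figures cannot be called impossible. It does not remove the problem, because those ceilings too are reached only if every non-HGSOC cancer is stage I/II, and nothing in the protocol supports that.

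A reader might also infer that the split contradicts the 70% advanced stage in section 1.1. The document does not support that. Section 1.1 describes patients nationally. The study enrols postmenopausal women referred with symptoms and with a raised CA125 or an imaged lesion, and their stage mix may differ.

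A reader might take 19 as the effective sample size for the whole primary outcome. It is not: it governs sensitivity only.

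It is fair to say that 19 is one multiplication away from the printed figures, and that section 5.7.1 already promises estimates, not a test. A power calculation may also sit in an analysis plan that is not at hand, so its absence is not part of this point.

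Finally, section 7.3 commits to reviewing the sample size calculations generally, so it cannot be said that the review would certainly miss a shortfall. What stands is that the only quantity it names is overall prevalence, which does not determine the information on primary sensitivity.

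**Conclusion.** The point holds in a limited form. The totals of 406 and 110 are correct. The overall stage split is compatible with the HGSOC figures only if essentially all 33 non-HGSOC cancers are stage I/II. At face value, 58 advanced HGSOC are set against 55 advanced cancers in total, and the early share has a ceiling of 47.5%.

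The protocol's own inputs give about 19 stage I/II HGSOC, with a range of 11 to 28 if prevalence and type mix are as assumed. A single sensitivity is then known to within about 20 percentage points either way. Prevalence could sit at 27% with as few as 11 such women.

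The stage arithmetic, the expected count and the interval widths rest on the protocol's figures and standard formulas. The power range of 23 to 33% is an illustration under assumed values, not a property of the protocol's plan.

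**What to change.** 1. In section 5.7.2, reconcile the overall stage split with the 70% and 25% HGSOC figures. Take the stage mix from the earlier ROCKeTS-GEN experience, which already supplies the prevalence, and not from the national figure in section 1.1.
2. State the expected number of stage I/II HGSOC (about 19, range 11 to 28 on the present inputs) and the resulting precision for sensitivity. Say that the sensitivity comparison will be reported as a paired difference with a 95% confidence interval. Note that specificity rests on the women without the target condition.
3. If power is mentioned, give it only as an illustration with its assumptions beside it.
4. In section 7.3, track the number of confirmed stage I/II HGSOC as well as overall ovarian cancer prevalence, blind to index test results.

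The cost is a text change, plus one more count in a review that is already planned. No extra patients are needed. The downside is that the stated expectation becomes less favourable.
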